### 9.0. STATISTICAL METHODS

Descriptive statistics (number of subjects, mean, SEM, median, interquartile limits, minimum and maximum) will be presented for quantitative variables. Ratings for categorical variables will be presented as counts and percentages. All tests of significance, unless otherwise stated, will be performed at alpha=0.05, two-sided.

Baseline comparisons for demographic characteristics between control and intervention groups will be completed with the Chi-square test, Fisher’s exact (two-tail) test, or analysis of variance (ANOVA), as appropriate.

Analysis of covariance (ANCOVA) will be used to assess differences among intervention groups in the primary and continuous secondary outcome variables at each post-randomization visit. The ANCOVA model will contain a term for intervention, with sex and baseline measures as covariates. Least squares mean values and corresponding SEM will be derived from the final ANCOVA model for each intervention group.

Counts and percentages of subjects who experience weight loss of  $\geq 5\%$  and  $\geq 10\%$  between baseline (Visit 2) and each post-randomization visit (visits 3, 4, 5, 6, and 7) will be presented. Differences among intervention groups in subjects with weight loss of  $\geq 5\%$  and  $\geq 10\%$  will be assessed using a generalized linear model with a logit link and binomial distribution specified. The model will contain a term for intervention, with sex as a covariate.

Differences among intervention groups in individual Satisfaction and Health/Well-being questionnaire scores will be assessed using a generalized linear model with a cumulative logit link and multinomial distribution specified. The model will contain a term for intervention, with sex and absolute change in weight as covariates.

For the analyses of body weight, body composition parameters, and body circumference parameters, each active group will be compared to the control group using a step-down Dunnett adjustment for multiple comparisons when a significant treatment effect is observed. Meanwhile,

no adjustments will be done on control vs. active comparisons on the remaining outcome variables.

Descriptive statistics will be provided for the Program Questionnaire outcomes. Also, linear association between change (absolute) in body weight from baseline (Visit 2; week 0) to end of study (Visit 7; week 16) and average meal replacements [averaged across Visits 4 to 7 (weeks 4-16)] will be obtained (spearman's rank-order correlation) for the MEDD and TSFL groups. Additionally, for the TSFL group, linear association between change (absolute) in body weight from baseline (Visit 2; week 0) to end of study (Visit 7; week 16) and number of coaching contacts will be obtained (spearman's rank-order correlation). Lastly, for the MEDD group, association between whether subjects made discretionary Nutrition Support contact(s) or not and weight loss of  $\geq 5\%$  will be assessed using a Fisher's exact test.

Assumption of normality of residuals will be investigated for each outcome variable at the 5% level of significance with the Shapiro-Wilk test (Shapiro 1965). If the normality assumption is not satisfied, then an analysis based on ranks will be performed.

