8.2.2. Outcome Analysis

Descriptive statistics [number of participants, mean, standard error of the mean (SEM), standard deviation, median, interquartile limits, minimum and maximum] will be presented for continuous variables. Ratings for categorical variables will be presented as counts and percentages.

Baseline comparisons for demographic characteristics between control and active groups will be completed with the Chi-Square test, Fisher's exact (two-tail) tests, or analysis ofvariance (ANOVA), as appropriate.

A mixed model repeated measures analysis of covariance (ANCOVA) will be used to assess differences between study groups in continuous outcome variables. Initial ANCOVA models will contain terms for intervention, week, intervention by week interaction, and sex, with baseline measures (where applicable) as covariates. Models will be reduced using a backward selection method until only significant terms and/or intervention and baseline measures (where applicable) remain in the model. Pairwise comparisons between groups at each post-randomization visit will be conducted from the final ANCOVA model, with Dunnett's correction for multiple comparisons between each Medifast group vs. control. Assumptions of normality of residuals will be investigated for each response measurement. If the normality assumption is rejected at the I% level with the Shapiro-Wilk test (Shapiro 1965), then an analysis using ranks or other transformation will be performed.

Counts and percentages of participants who experience weight loss of :0:5% or :0:10% between baseline and each post-randomization visit will be presented. Differences between control and each active group participants with weight loss :0:5% or :0:10% will be assessed using a generalized linear model with a logit link and binomial distribution specified. Initial repeated measures models will contain terms for intervention, week, intervention by week interaction, and sex. Models will be reduced using a backward selection method until only significant terms or intervention remains **in** the model. Pairwise comparisons at each post-randomization visit will be conducted using Dunnett's correction for multiple comparisons between each Medifast group vs. control.

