#### **10.0. MISSING OR INCOMPLETE DATA**

For the ITT population, a multiple imputation method will be implemented if the missing data mechanism is at least missing at random (MAR). Meanwhile, for the modified ITT population, analyses with and without imputation will be conducted. For this imputation, the method of Last Observation Carried Forward (LOCF) will be used as a single imputation approach (Elobeid MA et al, 2009). In this approach, if a subject's measurement is missing at a post-randomization visit, the value from the most proximal prior visit will be used for all missing visits afterwards. The imputation methods will only be applied to body weight. No imputations will be performed for other variables.

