#### **Changed to**

*For the ITT population, a multiple imputation method will be implemented if the missing data mechanism is at least missing at random (MAR). Meanwhile, for the modified ITT population, analyses with and without imputation will be conducted. For this imputation, the method of Last Observation Carried Forward (LOCF) will be used as a single imputation approach (Elobeid MA et al, 2009). In this approach, if a subject's measurement is missing at a post-randomization visit, the value from the most proximal prior visit will be used for all missing visits afterwards. The imputation methods will only be applied to body weights. No imputations will be performed for other variables.*

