### Population(s)

	Table 1	Subject Disposition
ITT	Table 2.1	Demographic Characteristics
ITT	Table 2.2	Vitals
ITT, mITT, Completers	Table 3	Primary Outcome Variable: Body Weight (Visit 7)
ITT, mITT, Completers	Table 4.1	Secondary Outcome Variables: Body Weight (Visits 3, 4, 5, 6)
ITT, mITT, Completers	Table 4.2	Secondary Outcome Variables: Weight Loss $\geq$ 5% and $\geq$ 10%
mITT, Completers	Table 4.3	Secondary Outcome Variables: Body Composition
mITT, Completers	Table 4.4	Secondary Outcome Variables: Body Circumference Parameters
mITT, Completers	Table 4.5	Secondary Outcome Variables: hs-CRP
mITT, Completers	Table 4.6	Secondary Outcome Variable: IWQOL-Lite Questionnaire Outcomes
mITT, Completers	Table 4.7	Secondary Outcome Variable: RAND Health Survey Questionnaire Outcomes
mITT, Completers	Table 4.8.1	Secondary Outcome Variables: Satisfaction and Health/Well-being Questionnaire
mITT, Completers	Table 4.8.2	Secondary Outcome Variables: Satisfaction and Health/Well-being Questionnaire (Recoded)
mITT, Completers	Table 4.9	Secondary Outcome Variables: Program Questionnaire

mITT, Completers	Table 4.10	Secondary Outcome Variable: Weight Loss Program Adherence
mITT, Completers	Table 4.11	Secondary Outcome Variable: Nutrition Support Contact
mITT	Table 5	Summary of Subjects with at Least One Intervention-Emergent Adverse Event

**Note: Tables 3, 4.1, and 4.2 will be generated for Completers, ITT population with multiple imputation applied for the missing data and for the mITT population, both with and without imputation. For the mITT population with imputation, LOCF imputation method applied for missing data will be reflected in footnotes of relevant tables. All other tables generated for the mITT population will be without imputation.**

Table 1  
Subject Disposition

---

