		Within group p-value+	x.xxx(r)	x.xxx(r)	x.xxx(r)
		LS Mean (SEM)	LS Mean (SEM)	LS Mean (SEM)	x.xxx(r)
		Group comparison p-value*		x.xxx(r)	
	Week 16	N	N	N	
	(Visit 7)	Mean (SEM)	Mean (SEM)	Mean (SEM)	
		Median	Median	Median	
		Q1, Q3	Q1, Q3	Q1, Q3	
		Min, Max	Min, Max	Min, Max	
	Change Week 16	N	N	N	
		Mean (SEM)	Mean (SEM)	Mean (SEM)	
		Median	Median	Median	
		Q1, Q3	Q1, Q3	Q1, Q3	
		Min, Max	Min, Max	Min, Max	
		Within group p-value+	x.xxx(r)	x.xxx(r)	x.xxx(r)
		LS Mean (SEM)	LS Mean (SEM)	LS Mean (SEM)	x.xxx(r)
		Group comparison p-value*		x.xxx(r)	
	% Change (Week 16)	N	N	N	
		Mean (SEM)	Mean (SEM)	Mean (SEM)	
		Median	Median	Median	
		Q1, Q3	Q1, Q3	Q1, Q3	
		Min, Max	Min, Max	Min, Max	

Table 4.3  
 Secondary Outcome Variable: Body Composition (Visits 4, 5, 6, 7) Descriptive Statistics and P-values

Parameter	Week	Control	TSFL	MEDD	Intervention p-value ^	
		Within group p-value+	x.xxx(r)	x.xxx(r)	x.xxx(r)	
		LS Mean (SEM)	LS Mean (SEM)	LS Mean (SEM)	LS Mean (SEM)	x.xxx(r)
		Group comparison p-value*		x.xxx(r)	x.xxx(r)	

^ p-values are from ANCOVA models, adjusted for sex and baseline values at Visit 2.

(r) indicates rank transformation was employed.

\* p-values are adjusted for multiple comparisons (each active group vs. control group)

+ p-values are generated from paired t-test or sign-rank test, as appropriate

**NOTE: This table will be presented for body composition measures: total fat mass, total lean mass, percent body fat, android fat and lean mass, gynoid fat and lean mass, and abdominal visceral fat mass and volume.**

Table 4.4  
Secondary Outcome Variables: Body Circumference Parameters (Visits 4, 5, 6, 7) Descriptive Statistics and P-values

Parameter	Week		Control	TSFL	MEDD	Intervention p-value^	
Waist Circumference (cm)	Baseline ( Week 0)	N	N	N	N		
	(Visit 2)	Mean (SEM)	Mean (SEM)	Mean (SEM)	Mean (SEM)	Mean (SEM)	
		Median	Median	Median	Median	Median	
		Q1, Q3	Q1, Q3	Q1, Q3	Q1, Q3	Q1, Q3	
		Min, Max	Min, Max	Min, Max	Min, Max	Min, Max	
	Week 4	N	N	N	N		
	(Visit 4)	Mean (SEM)	Mean (SEM)	Mean (SEM)	Mean (SEM)	Mean (SEM)	
		Median	Median	Median	Median	Median	

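### SAP 9.0 replaces the protocol's repeated-measures model with a separate ANCOVA at each visit, unlisted in Section 14, so several week-16 secondary contrasts ignore the earlier visits of participants who leave

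*SAP*

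**What the plan says.** **Protocol 8.2.2**: "A mixed model repeated measures analysis of covariance (ANCOVA) will be used to assess differences between study groups in continuous outcome variables". The starting terms are intervention, week, their interaction, sex and baseline. Then: "Models will be reduced using a backward selection method until only significant terms and/or intervention and baseline measures (where applicable) remain in the model". Visit-by-visit group comparisons come from that one final model.

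**SAP 9.0**: ANCOVA "will be used to assess differences among intervention groups in the primary and continuous secondary outcome variables at each post-randomization visit". The terms are intervention, sex and baseline. Failed normality leads to ranks: "If the normality assumption is not satisfied, then an analysis based on ranks will be performed".

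**SAP table shells (Section 17.0)**: the footnotes read "p-values are from ANCOVA models, adjusted for sex and baseline values at Visit 2".

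**SAP 10.0**, after planning multiple imputation (ITT) and LOCF (mITT) for weight: "No imputations will be performed for other variables". The note under the planned tables in Section 16.0 adds: "All other tables generated for the mITT population will be without imputation".

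**SAP 14.0** lists five changes from the protocol: populations, primary outcome, secondary outcomes, missing data and outliers. The missing-data item discloses the limit on imputation: "The imputation methods will only be applied to body weights". No item mentions the change of model.

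**The concern.** A likelihood-based repeated-measures model uses a participant's earlier values when the week-16 value is missing. A week-16 ANCOVA on observed values does not. Someone reading Section 14 learns that imputation is confined to weight, but could reasonably assume that the protocol's repeated-measures model still protects the other outcomes. The unlisted change removes that protection.

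At stake are the week-16 contrasts for body composition, circumferences and QoL. They can be biased in either direction if dropout depends on earlier response and its rate or mechanism differs between arms. The arms differ in coaching, supplied food and support, so equal dropout cannot be taken for granted. The data that would help are already collected.

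**Working it through.** **1. The plan's own figures (Protocol 8.1).** d = 9.0/15.0 = 0.60, with two-sided alpha 0.025 per comparison. Normal approximation: n = 2(2.241 + 0.842)²/0.60² = 52.8, so 53 per arm. With the t distribution (noncentrality 0.60 × √(55/2) = 3.15), power is 79.9% at 54 and 80.7% at 55, so 55 is reproduced. The attrition allowance is (66 − 55)/66 = 16.7%. The standard error of a two-arm difference at 55 per arm is √(2/55) = 0.19 SD. The model change alters none of these.

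**2. The two models.**

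| | Protocol 8.2.2 | SAP 9.0 |
|---|---|---|
| Structure | one model, all visits | ANCOVA at each visit |
| Week, intervention × week | yes | no |
| Backward selection | yes | no |
| In Section 14? | – | no |

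The shell footnotes fit the SAP model but do not prove it, because the protocol also calls its models ANCOVA. SAP 9.0 carries the point. SAP 13.0 covers departures from the SAP, not the SAP's departures from the protocol.

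**3. Who is affected.**

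| Outcome | Post-baseline weeks | Affected at week 16? |
|---|---|---|
| Body composition, circumferences | 4, 8, 12, 16 | yes, up to three earlier values unused |
| QoL | 8, 16 | yes, one earlier value unused |
| Weight, mITT without imputation | 2, 4, 8, 12, 16 | yes |
| Weight, ITT | same | no, multiple imputation planned |
| hs-CRP | 16 | no, no earlier post-baseline value to use |

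**4. Size (simulation, 400,000 per arm).** From the plan: 16.7% dropout, d = 0.60. Assumed:
- change is normal with SD 1, and the effect grows linearly to week 16;
- correlations of weeks 4/8/12 with week 16 are 0.59/0.81/0.88 (among earlier visits 0.75, 0.66, 0.90) or 0.34/0.49/0.70 (0.70, 0.49, 0.70);
- after each earlier visit, logit P(leave) = a + ln(OR) × current change, OR 1.5-3 per SD of poorer response;
- nobody who leaves returns at week 16.

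Shift = observed week-16 difference minus full-data difference, without sex or baseline terms:

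| Dropout | Body composition, circumferences (SD) | QoL (SD) | Direction |
|---|---|---|---|
| Response-driven, 16.7% in each arm | ≤0.003 | ≤0.001 | – |
| One shared rule | 0.005-0.033 | 0.002-0.026 | too small |
| Response-driven in active arm only | 0.035-0.126 | 0.032-0.126 | too large |
| Response-driven in control only | 0.037-0.130 | 0.033-0.126 | too small |

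If half of those who leave attend week 16, the shared rule gives 0.001-0.013 and active-only 0.014-0.057. With a true effect of 0.30 SD, active-only for body composition is still 0.035-0.129. One-arm bias is therefore additive and should be read in SD, not as a percentage of an effect. The shared-rule figure depends on the set-up: a variant with sex and baseline terms and wider dropout rates (20.2% control, 13.1% active) gave 9.0% of 0.60 = 0.054 SD at OR 3.

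**5. Early leavers.** Let dropout after weeks 2, 4, 8 or 12 follow weight in the active arm only, OR 2-3. Assume correlations of 0.9 per four weeks, and outcome-weight correlations of 0.5-0.8 (body composition) and 0.30-0.45 (QoL). Then 28-30% of those who leave have no post-baseline body-composition value, and 55-57% have no post-baseline QoL value.

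| Shift (SD) | ANCOVA | Repeated measures, outcome only | With weeks 2-12 weight |
|---|---|---|---|
| Body composition | 0.046-0.107 | 0.012-0.033 | ≤0.001 |
| QoL | 0.029-0.059 | 0.015-0.036 | ≤0.002 |

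Another covariance choice for QoL gave 9.3%, 7.9% and 0.4% of 0.60, that is 0.056, 0.047 and 0.002 SD. For QoL the outcome-only model thus removes roughly 15% to 50% of the shift.

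**6. Backward selection.** If it dropped intervention × week, one average would replace the week-16 contrast. Under linear growth over weeks 4-16 that average is (0.25 + 0.50 + 0.75 + 1.00)/4 = 62.5% of it.

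**The case against.** The strongest reply is that this is mainly a documentation gap. The primary outcome is week-16 weight, and the ITT analysis plans multiple imputation, although conditional on missingness at random. The mITT weight table without imputation stands beside imputed and completer tables, so it serves as a sensitivity display. The bias needs dropout that differs between arms, and nothing in the documents favours that. Even the largest illustrated shift, 0.13 SD, is below one standard error. Protocol 6.7 and 10.5 plan an attempted visit at week 16 after withdrawal, and the 16.7% is an allowance, not a forecast of missing week-16 data. The precision gain from repeated measures is small: about 2-5% in the standard error for body composition and 1-2% for QoL when missingness depends on arm only.

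All of that stands, and it limits the weight of the point. It does not explain why the change is unlisted when Section 14 records smaller edits, such as adding body composition to the outlier check. Nor does it give a reason to leave collected visits unused.

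Three stronger readings are tempting and unsupported. A reader might infer that the primary ITT result loses its protection; multiple imputation is planned for it. A reader might infer that the secondary results will be biased by a set share of the effect; the plan's d = 0.60 is for weight, no effect size is given for the other outcomes, and where the rank rule applies these mean differences do not carry over. A reader might infer that restoring the protocol's model is enough; its backward selection can remove the week-16 contrast, and for QoL the outcome-only model helps little.

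**Conclusion.** The model change, its absence from Section 14 and the loss of earlier visits from the affected week-16 contrasts follow from the text and are certain. The size of any bias is not. It is about zero if response-driven dropout is equal across arms. Under the assumptions in step 4 it is about 0.01-0.03 SD with one shared rule and 0.04-0.13 SD (from 0.03 for QoL) if response-driven in one arm only, and smaller with week-16 attendance after withdrawal. The documents do not say which case applies. This is worth correcting because the remedy is cheap and close to what the protocol planned; it is not a threat to the primary ITT analysis.

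**What to change.** - **SAP 9.0**, continuous outcomes with two or more post-baseline visits, including the mITT weight tables without imputation: use a repeated-measures model with fixed intervention, visit, intervention-by-visit, sex, baseline and baseline-by-visit terms. Use unstructured covariance, with a fallback named in advance, and no backward selection. Report the Visit 7 contrast of each Medifast arm against control.
- **QoL**: add multiple imputation that includes weeks 2-12 weight. Use the same imputation as a sensitivity analysis for body composition and circumferences.
- **hs-CRP**: keep ANCOVA.
- **Rank rule**: leave as planned, and report the repeated-measures estimate alongside it.
- **Section 14**: list and justify the model change, together with the other unlisted changes. These are: responder models no longer repeated-measures; backward selection dropped; Dunnett changed to step-down, conditional on a significant treatment effect and for some outcomes only; Shapiro-Wilk level moved from 1% to 5%.

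Cost: SAP text, some programming and a convergence check. No new data and no change to conduct. A sponsor who prefers ANCOVA at each visit should still list and justify it.

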The interventions in this study are designed to mimic the TSFL and MEDD user experiences and will utilize the meal plans, Medifast products, and support options available for each of these programs. The TSFL and MEDD groups will be compared to a control group following a self-directed, food-based, reduced-calorie diet consistent with the 2015 Dietary Guidelines for Americans and based on the United States Department of Agriculture (USDA) ChooseMyPlate program.

4. Objectives

The primary objective of this study is to evaluate the effects of two commercially available weight loss programs, the TSFL and the MEDD programs, each compared to a self-directed control diet, on changes in body weight over a 16-week weight loss phase, in apparently healthy overweight and obese men and women.

Secondary objectives include, examining effects of each weight loss program compared to the seli directed control diet on changes in body composition, body circumference parameters, QoL, and biomarkers of inflammation over a 16-week weight loss phase. Relationships between changes in body weight with self-reported adherence and QoL assessments will also be examined. Additionally, participant perspectives on program satisfaction and sense of health/well-being will be assessed at the end of the study.

5. Study Sample

Participants will be apparently healthy men and women, 18-65 years of age, inclusive, each with a body mass index (BMI) of 27.0 to 42.0 kg/m², inclusive. No more than 10% of participants will be enrolled with a BMI 27.0 kg/m² and <30.0 kg/nl and no more than 25% of participants will be males.

6. Study Design and Procedures

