Counts and percentages for questionnaire responses will be presented by intervention group for ordinal outcomes (e.g. Likert scales). Differences between control and each active group will be assessed using a generalized linear model with a cumulative logit link and multinomial distribution specified. Initial repeated measures models will contain terms for intervention, week, intervention by week interaction, and sex. Models will be reduced using a backward selection method until only significant terms or intervention remains in the model. Pairwise comparisons between control and each active group at each post-randomization visit will be conducted using Dunnett's correction for multiple comparisons between each Medifast group vs. control.

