## 8.0. OUTCOME ANALYSIS

### 8.1. Primary Outcome Variable

The primary outcome variable will be change (absolute and percent change) in body weight from baseline (Visit 2; week 0) to end of study (Visit 7; week 16)

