	LS Mean (SEM)	LS Mean (SEM)	LS Mean (SEM)	LS Mean (SEM)	x.xxx(r)
	Group comparison p-value*		x.xxx(r)	x.xxx(r)	

^ p-values are from ANCOVA models, adjusted for sex and baseline values at Visit 2

(r) indicates rank transformation was employed.

\* p-values are adjusted for multiple comparisons (each active group vs. control group)

+ p-values are generated from paired t-test or sign-rank test, as appropriate

Table 4.2  
Secondary Outcome Variables: Weight Loss  $\geq 5\%$  and  $\geq 10\%$  (Visits 3, 4, 5, 6, 7)

Parameter	Week	Control	TSFL	MEDD	Intervention p-value ^	
Weight Loss responders (% change <math>\geq 5\%</math>)	% Change Week 2 (Visit 3)	N (%)	N (%)	N (%)	x.xxx	
	Group comparison p-value*		x.xxx	x.xxx		
	% Change Week 4 (Visit 4)	N (%)	N (%)	N (%)	x.xxx	
	Group comparison p-value*		x.xxx	x.xxx		
	% Change Week 8 (Visit 5)	N (%)	N (%)	N (%)	x.xxx	
	Group comparison p-value*		x.xxx	x.xxx		
	% Change Week 12 (Visit 6)	N (%)	N (%)	N (%)	x.xxx	
	Group comparison p-value*		x.xxx	x.xxx		
	% Change Week 16 (Visit 7)	N (%)	N (%)	N (%)	x.xxx	
	Group comparison p-value*		x.xxx	x.xxx		
	Weight Loss responders (% change <math>\geq 10\%</math>)	% Change Week 2 (Visit 3)	N (%)	N (%)	N (%)	x.xxx
		Group comparison p-value*		x.xxx	x.xxx	
		% Change Week 4 (Visit 4)	N (%)	N (%)	N (%)	x.xxx
		Group comparison p-value*		x.xxx	x.xxx	
% Change Week 8 (Visit 5)		N (%)	N (%)	N (%)	x.xxx	
Group comparison p-value*			x.xxx	x.xxx		
% Change Week 12 (Visit 6)		N (%)	N (%)	N (%)	x.xxx	
Group comparison p-value*			x.xxx	x.xxx		
% Change Week 16 (Visit 7)		N (%)	N (%)	N (%)	x.xxx	
Group comparison p-value*			x.xxx	x.xxx		

^ p-values are from GLM models with a logit link and binomial distribution specified and sex as a covariate

\* p-values are adjusted for multiple comparisons (each active group vs. control group)

Table 4.3  
Secondary Outcome Variable: Body Composition (Visits 4, 5, 6, 7) Descriptive Statistics and P-values

Parameter	Week	Control	TSFL	MEDD	Intervention p-value^	
Total Fat Mass (kg)	Baseline ( Week 0) (Visit 2)	N	N	N	N	
		Mean (SEM)	Mean (SEM)	Mean (SEM)	Mean (SEM)	
		Median	Median	Median	Median	
		Q1, Q3	Q1, Q3	Q1, Q3	Q1, Q3	
		Min, Max	Min, Max	Min, Max	Min, Max	
	Week 4 (Visit 4)	N	N	N	N	
		Mean (SEM)	Mean (SEM)	Mean (SEM)	Mean (SEM)	

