		Min, Max	Min, Max	Min, Max	Min, Max	
	Change Week 16	N	N	N	N	
		Mean (SEM)	Mean (SEM)	Mean (SEM)	Mean (SEM)	
		Median	Median	Median	Median	
		Q1, Q3	Q1, Q3	Q1, Q3	Q1, Q3	
		Min, Max	Min, Max	Min, Max	Min, Max	
	Within group p-value+	x.xxx(r)	x.xxx(r)	x.xxx(r)		

Table 4.7  
 Secondary Outcome Variable: RAND Questionnaire Outcomes (Visits 5 and 7) Descriptive Statistics and P-values

Parameter	Week	Control	TSFL	MEDD	Intervention p-value ^
		LS Mean (SEM)	LS Mean (SEM)	LS Mean (SEM)	x.xxx(r)
		Group comparison p-value*		x.xxx(r)	x.xxx(r)

^ p-values are from ANCOVA models, adjusted for sex and baseline values at Visit 2.

(r) indicates rank transformation was employed.

\* p-values are NOT adjusted for multiple comparisons (each active group vs. control group)

+ p-values are generated from paired t-test or sign-rank test, as appropriate

**NOTE: This table will be presented for the eight scale scores of the RAND questionnaire (Physical functioning, Role limitations due to physical health, Role limitations due to emotional Problems, Energy/fatigue, Emotional well-being, Social functioning, Pain, General health).**

Table 4.8.1  
 Secondary Outcome Variable: Satisfaction and Health/Well-being Questionnaire Descriptive Statistics

Parameter	Week	Rating	Control	TSFL	MEDD
Recommend Weight Loss Plan	Week 16 (Visit 7)	Strongly Disagree	N (%)	N (%)	N (%)
		Disagree	N (%)	N (%)	N (%)
		Neither Agree or Disagree	N (%)	N (%)	N (%)
		Agree	N (%)	N (%)	N (%)
		Strongly Agree	N (%)	N (%)	N (%)

NOTE: This table will be presented for ratings for each question of the Satisfaction and Health/Well-being questionnaire.

Table 4.8.2  
 Secondary Outcome Variable: Satisfaction and Health/Well-being Questionnaire (Recoded) Descriptive Statistics and P-values

Parameter	Week	Rating	Control	TSFL	MEDD	Intervention p-value
Recommend Weight Loss Plan	Week 16 (Visit 7)	Disagree	N (%)	N (%)	N (%)	x.xxx
		Neither Agree or Disagree	N (%)	N (%)	N (%)	
		Agree	N (%)	N (%)	N (%)	
		Group comparison p-value*		x.xxx	x.xxx	

\* p-values are NOT adjusted for multiple comparisons

NOTE: This table will be presented for ratings for each question of the Satisfaction and Health/Well-being questionnaire.

Table 4.9  
Secondary Outcome Variable: Program Questionnaire (Visits 4, 5, 6, 7) Descriptive Statistics

Parameter	Week		Control	TSFL	MEDD
Physical Activity Level	Baseline ( Week 0)	N	N	N	N
	(Visit 2)	Mean (SEM)	Mean (SEM)	Mean (SEM)	Mean (SEM)

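### The only planned test of the satisfaction and well-being items adjusts for weight change, a post-randomisation outcome, so it does not estimate the programs' total effect on them.

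*SAP*

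**What the plan says.** SAP 9.0 tests each Satisfaction and Health/Well-being item with a cumulative-logit model: "The model will contain a term for intervention, with sex and absolute change in weight as covariates". The questionnaire is completed once, at Visit 7. SAP 8.2 collapses its five response levels to three, and Table 4.8.2 reports the tests on the collapsed ratings. Table 4.8.1 gives counts only.

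On the covariate itself, SAP 8.1 states: "The primary outcome variable will be change (absolute and percent change) in body weight", measured from Visit 2 to Visit 7.

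For ordinal questionnaire items, Protocol 8.2.2 specifies a model without weight change: "Initial repeated measures models will contain terms for intervention, week, intervention by week interaction, and sex". None of the five changes listed in SAP 14.0 concerns this model.

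The aim in Protocol 4 is that "participant perspectives on program satisfaction and sense of health/well-being will be assessed at the end of the study". It does not mention equal weight loss.

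The Table 4.8.2 footnote says only that "p-values are NOT adjusted for multiple comparisons". By contrast, the Table 4.2 footnote names its covariate: "p-values are from GLM models with a logit link and binomial distribution specified and sex as a covariate".

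**The concern.** Weight change lies on the path from program to rating. Several items in Protocol Appendix 6 ask about things that follow from losing weight, such as how clothes fit, whether the plan worked and whether real success was achieved. With weight change in the model, the intervention term compares arms among people who lost the same amount. That leaves out whatever the program achieved by producing more weight loss.

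It is not a clean direct effect either. Weight loss is not randomised and probably shares causes, such as motivation, with the ratings. Conditioning on it then links arm to those causes.

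Table 4.8.2 would print raw percentages by arm, which show the total difference, beside p-values that answer another question, with no note to say so. A program rated better because it works could show clearly better percentages and a null p-value. The SAP would also be inconsistent across similar constructs. The quality-of-life scales, including self-esteem and emotional well-being, are adjusted only for sex and baseline, while satisfaction items on feeling better about oneself and on overall well-being are also adjusted for weight change.

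**Working it through.** **Inputs from the plan.** Difference 9.0 lb and SD 15.0 lb, so d = 9.0/15.0 = 0.60; 55 evaluable per group (SAP 3.0). Two-sided 0.05 for these tests (SAP 9.0). Three response levels (SAP 8.2). 20 items (Protocol Appendix 6). At most 25% men (SAP 3.0). The documents give no link between weight loss and ratings, so all path strengths below are assumptions.

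**1. The plan's own figure.** n per arm = 2(z₀.₉₈₇₅ + z₀.₈₀)²/d² = 2(2.241 + 0.842)²/0.36 = 52.8, so 53 by the normal approximation. At 55 per arm the t-test power is 80.7%. Attrition allowance: 165/(1 − 1/6) = 198. The sample size reproduces. The trial is therefore built to separate the arms on the very variable used here as a covariate.

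**2. What each model estimates.** Let A = 1 for a program and 0 for control. Let W be weight loss in SD units, with mean 0.60A. Let U be an unmeasured shared cause that explains a fraction f of the within-arm variance of W. Let the logit of a better rating be cA + bW + gU.
- Total program effect on this scale: c + 0.60b.
- Intervention term with W in the model: c − 0.60·g·√f.

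With c = 0, b = 1 and no shared cause, the total is 0.60 and the adjusted term is 0. Leaving W out flattens the logit slope to about 0.60 × √(3.29/(3.29 + 1)) = 0.525, so the expected odds ratio (OR) is about exp(0.525) = 1.69 without W and 1.00 with it. With g = 0.7, the shared-cause shift is 0.60 × 0.7 × √0.20 = 0.188 (OR about 0.83) for f = 20%, and 0.60 × 0.7 × √0.05 = 0.094 (OR about 0.91) for f = 5%.

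**3. Simulation.** Three-level proportional-odds models with intervention and sex (25% male), with and without W. ORs come from 2 × 200,000 participants, with cut-points −1 and 0.5; two other cut-point pairs moved no OR by more than 0.02. Rejection rates come from 1,500 comparisons of 55 v 55 (Monte Carlo SE about 1 point).

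| Assumed path | OR without W → with W | Chance of p<0.05 without W → with W |
|---|---|---|
| Wholly through weight (b = 1.0) | 1.65 → 1.00 | 31% → 5% |
| Through weight plus direct benefit (c = 0.6) | 2.74 → 1.82 | 81% → 33% |
| Item unrelated to weight, no shared cause | 1.83 → 1.82 | 40% → 36% |
| Through weight, shared cause f = 5% | 1.58 → 0.92 | not run |
| Through weight, shared cause f = 20% | 1.56 → 0.85 | not run |
| Same, f = 20%, plus c = 0.19 | 1.79 → 1.01 | not run |

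**4. Range.** A smaller simulation (400 comparisons of 55 v 55 per setting, error about 1 to 2.5 points) varied the inputs.
- Effect wholly through weight, b = 0.5 / 1.0 / 1.5: OR 1.32 / 1.71 / 2.01 without W and 0.96 / 1.05 / 1.04 with it. Rejection 12% / 29% / 47% without W and 6% / 5% / 5% with it.
- Opposing direct effect (c = −0.6, b = 1.0): OR 0.97 with 5% rejection without W, and 0.50 with 38% rejection with it.
- No program effect on the item, but a strong shared cause (correlation 0.5 with weight loss, log-odds 1): the test without W rejects 4%. The test with W rejects 9% at a 9 lb difference and 21% at 15.5 lb, the prior study's difference (29.8 − 14.3).

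**5. Tests affected.** 20 items × 2 active arms = 40 comparisons, plus 20 overall intervention p-values, in each of the two populations listed for Table 4.8.2.

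**The case against.** No document says that the target for these items is the total effect. Protocol 4 asks for comparison with control on other secondary outcomes, and for satisfaction says only that perspectives will be assessed. Raw distributions by arm meet that aim whatever model is used, and satisfaction at equal weight loss is a legitimate question. That would justify a labelled supplementary analysis. It does not justify making it the only test, unexplained.

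About 8 of the 20 items concern features of the plan, such as convenience, support and tools, where weight loss is a less obvious mediator. This stands as a limit on how many items are badly affected. But the adjustment leaves such items nearly unchanged only when there is no shared cause. With f = 20% and g = 0.7, an item with no weight path and no program effect had an adjusted OR of about 0.84 to 0.88, against 1.00 unadjusted.

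Reversal is weak at this trial's size. With the moderate shared causes above, the adjusted test at 55 per arm rejected 8–10% (f = 20%) or 6–7% (f = 5%) of the time. That also stands: the realistic harm is a missed difference more than a reversed one.

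The visit for weight change is not named in this sentence, but Visit 7 is the only sensible reading. SAP 14.0 also omits other model changes, so the missing declaration is not peculiar to this model. Finally, this is one secondary outcome without multiplicity control, and it is already limited to respondents: "No imputations will be performed for other variables" beyond body weight.

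**Conclusion.** The concern holds. As written, the satisfaction tests do not estimate the programs' total effect on these items, and no stated aim supports the equal-weight-loss comparison they make. For items that depend on weight loss the loss is large: at the planned 0.60 SD difference, a wholly weight-mediated effect disappears (OR 1.65 to 1.00), and an effect with an added direct benefit loses more than half its chance of detection (81% to 33%). These sizes rest on assumed path strengths. The direction of error is not fixed, since an opposing direct effect or a shared cause can create an apparent difference. The damage is confined to the p-values of one secondary outcome. The primary analysis and the raw counts in Tables 4.8.1 and 4.8.2 stay valid. It should be fixed before analysis.

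**What to change.** - In SAP 9.0, make the cumulative-logit model with intervention and sex, without weight change, the analysis for Table 4.8.2. Apply it to the 20 overall p-values as well as the 40 active-versus-control comparisons. The protocol's week terms do not apply to a questionnaire given once.
- If satisfaction beyond weight loss is of interest, report the weight-adjusted model in a separate table labelled exploratory. Name Visit 7 as the visit for weight change, and state the assumption of no unmeasured common cause of weight change and satisfaction.
- Record the difference from the protocol's model in SAP 14.0, and list the covariates in the Table 4.8.2 footnote.

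The cost is one sentence, one entry in the list of changes and one footnote, with one extra table if the adjusted model is kept. No new data are needed. If the adjusted model is dropped, the SAP no longer addresses satisfaction beyond weight loss.
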